4. STUDY POPULATION

4.1 Population (base)

Patients with newly diagnosed prostate cancer, who have proven synchronous metastatic disease on PSMA PET/CT. Recruitment will take place in the urologist outpatient clinics. Patients will be approached for participation in the study at their first outpatient contact. They will sign informed consent after their diagnosis and management has been discussed at a multidisciplinary meeting.

4.2 Inclusion criteria

In order to be eligible to participate in this study, a subject must meet all of the following criteria:

- Men >18 years of age.
- Mentally competent and understanding of benefits and potential burden of the study.
- Written and signed informed consent.
- Histological confirmed diagnosis of adenocarcinoma of the prostate.
- Indicated to start on hormonal therapy (any LHRH agonist or antagonist).
- Indicated to start on upfront therapy (i.e. docetaxel, abiraterone, apalutamide, or enzalutamide).
- Any initial PSA.
- Any Gleason score.
- Any T-stage.
- Any N-stage.
- Stage M1, with multiple / high volume metastasis:More than three (>3) metastatic lesions (any combination of either lymph node metastasis outside of pelvis, bone metastasis, or visceral metastasis), as seen on PSMA-PET/CT-imaging. As these patients are treated with palliative intent.

4.1 Exclusion criteria

A potential subject who meets any of the following criteria will be excluded from participation in this study:

- Concomitant malignancy (except from BCC of the skin).
- History of prior diagnosed or treated PCa.
- Any unrelated illness (e.g. active infection, inflammation or laboratory abnormalities)
 that in the judgment of the investigator will significantly affect patient's clinical status
 and/or outcome of the study.
- Any known allergy for the upfront therapy.
- Any known allergy for LHRH agonist or antagonist.

4.2 Sample size calculation

Predictive modelling will be used. Besides the parameter of main interest:PSMA-PET/CT response to upfront therapy based on PERCIST (i.e. Complete response (CR), Partial response (PR), Progressive disease (PD), Stable disease (SD)) see also chapter 5.1.1 table 1, the following potential predictive factors will be taken into account (these variables have been included in subgroup analyses in earlier M+HSPC studies):

- PSA at diagnosis.
- Pathological Gleason score (ISUP Gleason grades 1-3 versus 4-5).

- Metastasis volume load (defined as 'Charteed'-study criteria; high volume defined as >5 skeletal lesions with 1 or more outside pelvis or vertebrae or visceral metastasis, low volume defined as all others).(Sweeney 2015)

- PSA response (defined as PSA nadir).
- Type of upfront therapy used.
- PSMA response to hormonal therapy as continues variable in percentage based on PERCIST (see 5.1.1).

Estimation of proportion of variation in PERCIST PSMA response was based on preliminary case series on PSMA response in M+HSPC patients.(Seitz 2018).

[figure not shown]
Sample size estimation was performed in SAS (version 9.4) PROC POWER, using a score test for a Cox proportional hazards model.

Considerations (Figure 2):

- Expected median time to CRPC: 24 months.
- Power 80%.
- Type I error (alpha) 5%, two-sided.
- Probability of event within 24 months: 0.5.
- Estimation of proportion of variation in PERCIST PSMA response (R²): 0.75 (based on linear regression of data from Seitz et al.).
- Standard deviation PERCIST PSMA response: 3.5 4 (per 10 percentage points).
- Small to medium effect (hazard ratio 1.2-1.3 per 10 percentage points PERCIST PSMA).

Assuming a standard deviation of 4, an R² of 0.75, and a hazard ratio of 1.2-1.3, the number needed to include is 150.

Around 1750 new diagnoses of M+HSPC are made in The Netherlands yearly. The collaborating centres cover ~12.5% of new diagnoses in The Netherlands (~200 cases). Assuming a study acceptance rate of 50% (low estimation), patient accrual (N=150) is expected to cover ~18 months.

[figure not shown]

Fig. 2 Considering small effect HR 1.2 - 1.3, SD 4, R-square 0.75 - 0.80 leads to sample size 130 - 150.

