WMO Medical Research Involving Human Subjects Act; in Dutch: Wet Medisch-

wetenschappelijk Onderzoek met Mensen

Ga Gallium-68AE Adverse EventAR Adverse Reaction

CT Computed Tomography IB Investigator's Brochure

METC Medical research ethics committee (MREC); in Dutch: medisch ethische

toetsing commissie (METC)

MRI Magnetic Resonance Imaging

mSv MilliSievert
PCa Prostate Cancer

PERCIST PET Response Evaluation Criteria In Solid Tumours

PET Positron Emission Tomography

PET-based MaNagement of Metastasized prostate cancer treated with

MaN Novel therapies

PSA Prostate-Specific Antigen.

PSMA Prostate-Specific Membrane Antigen

RECIST Response Evaluation Criteria in Solid Tumours

(S)AE (Serious) Adverse Event

SUSAR Suspected Unexpected Serious Adverse Reaction

WMO Medical Research Involving Human Subjects Act (in Dutch: Wet Medisch-

wetenschappelijk Onderzoek met Mensen

SUMMARY

Rationale: Men, newly diagnosed with metastasized prostate cancer on PSMA PET/CT, who start on standard hormonal therapy, are additionally treated with either upfront chemotherapy or upfront extra androgen-receptor targeted agents ('ARTA'), as per guidelines' recommendations. The benefit in overall survival of these two options is similar, but important differences exist in patient-specific efficacy, costs, side-effects, and impact on quality of life. No predictive factors are available to individualize treatment choice. Currently, a one-size-fits-all strategy with hormonal therapy plus chemotherapy is usually followed.

Objective: To assess the predictive value of early response measurements on PSMA-PET/CT for therapy success, defined as time to development of castration-resistant prostate cancer (CRPC), in order to personalize treatment choice.

Study design: Prospective, single arm, open label, non-interventional, non-therapeutic observational cohort study.

Study population: Patients >18 years with newly diagnosed, histologically proven prostate cancer with >3 skeletal or visceral metastatic lesions on the PSMA-PET/CT, who are considered eligible for upfront therapy (chemotherapy or ARTA) in addition to standard hormonal therapy.

Main study parameters/endpoints:

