2. OBJECTIVES

The primary objective of the current research proposal is to assess whether PSMA-PET/CT early response assessment (between start of upfront therapy and after 2 months of upfront therapy) is associated with treatment success (defined as time to development of CRPC). This may allow for individualized treatment planning in newly diagnosed M+ HSPC patients, who have started on ADT and receive additional upfront therapy (Figure 1).

By performing PSMA PET/CT at fixed time points during ADT and upfront therapy treatment, information is collected on the imaging–based response to treatment. Analysis of the value of PSMA-PET/CT will be assessed by predictive modelling, taking the following predictive factors into account: PET findings, PSA at diagnosis, pathological Gleason score, tumour load, and PSA early response.

The secondary objectives include:

- Predictive value of baseline PSMA-PET/CT imaging on time to development of CRPC.
- Predictive value of early response to ADT only (which is standard of care during first 2-3 months of therapy; upfront therapy needs to be started within this timeframe) on time to development of CRPC.
- Analysis of response in different subgroups of patients: high versus low tumour load, high versus low PSA, high versus low Gleason score, <median versus >median age at diagnosis.

* Primary predictor: Upfront therapy PSMA response

Fig. 1 PET-MaN study design. (SOC = standard of care) Imaging will include PSMA-PET/CT at standardized time points (instead of at progression / on indication only): 1st baseline, 2nd after 2 months of hormonal therapy (ADT), and 3rd after 2 months of upfront therapy (for docetaxel, this is between 3rd and 4th cycle (out of 6)).

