3. STUDY DESIGN

The study is a prospective open-label, non-interventional, non-therapeutic observational cohort study. The study is performed in an outpatient setting. Total study duration will be 48 months.

Multicenter (Netherlands):

- UMC Utrecht, Utrecht (lead);
- St Antonius Hospital, Utrecht / Nieuwegein (external inclusion);
- Meander MC, Amersfoort (external inclusion);
- Amsterdam UMC, Amsterdam (external inclusion).

Patients will be treated with hormonal therapy plus upfront therapy. Indication for upfront therapy and the choice for specific combination will be made at a multidisciplinary meeting. Patients are elected for study participation after prostate cancer has been histologically confirmed and signs of multiple metastases have been confirmed on PSMA-PET/CT-imaging. The definition of multiple / high volume metastasis is: >3 metastatic lesions (any combination of either lymph node metastasis outside of pelvis, bone metastasis, or visceral metastasis). Participating centers will standard use PSMA PET/CT as first imaging choice at suspicion of metastasized disease.

Standardized imaging (Figure 1):

- PSMA-PET/CT:
 - 1. Standard of care PSMA PET/CT: At diagnosis (hormonal therapy needs to be started <4 weeks).
 - 2. Additional PSMA PET/CT: 2 months after start hormonal therapy (+/- 1 week).
 - 3. Additional PSMA PET/CT: 2 months after start of chemotherapy (+/- 1 week).

Patients continue hormonal therapy plus upfront therapy according to standard of care. Follow-up of standard of care consists of monthly outpatient checks, including standard lab tests (i.e. PSA, AF, testosterone, electrolytes, full blood count).

The results of the additional PSMA-PET/CT scans will not be blinded to patients or physicians and will not be used in clinical decision-making.

The primary endpoint is time from start of ADT to CRPC. CRPC is defined by EAU guidelines (Cornford 2020) as:

Castrate serum testosterone <50 ng/dL or 1.7 nmol/L plus either:

- a. Biochemical progression: Three consecutive rises in PSA at least one week apart resulting in two 50% increases over the nadir, and a PSA >2 ng/mL, or:
- b. Radiological progression: The appearance of new lesions: either two or more new bone lesions on skeletal scintigraphy or a soft tissue lesion on CT using RECIST (Response Evaluation Criteria in Solid Tumours) or on (PSMA-)PET/CT-imaging using PERCIST (PET Response Evaluation Criteria In Solid Tumours) (Fanti 2020, Boellaard 2015).

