5.2.1 PSMA-PET/CT imaging protocol

PSMA-PET/CT will be performed according to standard of care, with low-dose CT using 1.5-2.0 MBq/kg of PSMA-tracer (68-Gallium PSMA and 18 Fluor PSMA are allowed). Image reconstruction will be performed according to EARL accreditation.(Boellaard 2015) The used PSMA tracer may vary between participating centers, but in each center the same tracer will be used at baseline and during follow-up. Image acquisition starts 60 minutes (+/- 15 minutes is acceptable) after injection from head to upper thigh. Effective absorbed dose is approximately 6 mSv, which is similar to a full-dose CT scan of the abdomen. IV drip is necessary to inject the tracer.

The scans will be examine by the local nuclear medicine physician and afterwards two experienced nuclear medicine physicians will examine all PSMA-PET/CT images. The following parameters will be assessed:

- TNM stage.
- Response according to PERCIST (in follow-up scans).
- PiP-RADS scores.
- Location and number of prostate lesions, lymph node metastases and distant metastases.
- Activity (SUVIbm-mean, SUVIbm-peak, SUVIbm-max) of all lesions.

5.2.1.1 Timing first PSMA-PET/CT – baseline First PSMA-PET/CT needs to be performed <4 weeks before start ADT.

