7. STATISTICAL ANALYSIS

7.1 Primary study parameter(s)

The collected data will include nominal, categorical, ordinal and continuous variables.

A predictive model will be constructed. Main parameter is PERCIST PSMA response to upfront therapy. Main outcome is time since diagnosis to development of CRPC. Primary analysis will be the comparison of two Cox proportional hazards models for time to development of CRPC: the first including the six predictive factors (PSA at diagnosis, pathological Gleason score, metastasis volume load, PSA early response, type of upfront therapy, PSMA response to hormonal therapy only), mentioned in section 4.4, and the second including those six variables plus PERCIST PSMA-PET/CT response after start of upfront therapy. The models will be compared using a likelihood ratio test, and the c-statistic will be calculated to estimate the added benefit of PERCIST PSMA response above the known predictors of CRPC.

An intention-to-treat analysis will be performed (i.e. all subjects who actually receive baseline and two follow-up PSMA PET/CT scans.) will be included for analysis, even when treatment is changed early.

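### Baseline tumour extent enters both primary Cox models only as a high/low split, so the test of PET response may pick up baseline extent; log lesion count should be added to both models

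*Combined protocol and SAP*

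**What the plan says.** - **Load factor.** Section 4.2 (Sample size calculation) lists the predictive factors. Metastasis volume has two levels: "high volume defined as >5 skeletal lesions with 1 or more outside pelvis or vertebrae or visceral metastasis, low volume defined as all others".
- **Primary analysis.** Section 7.1 compares two nested Cox models for time to CRPC, "the first including the six predictive factors (PSA at diagnosis, pathological Gleason score, metastasis volume load" and three more: PSA early response, type of upfront therapy, and PSMA response to hormonal therapy). The second model adds PERCIST PSMA response to upfront therapy. A likelihood ratio test and the c-statistic are to show what that response adds to the known predictors. (Section 7.1 points to a section 4.4 for the list; it stands under Sample size calculation.)
- **Data on extent.** Section 5.2.1 has the readers record "Location and number of prostate lesions, lymph node metastases and distant metastases", along with the SUV of every lesion. No count enters the primary models. Baseline PET appears only as a separate secondary analysis (sections 5.1.2 and 7.2).
- **Entry rule.** Section 3 states "The definition of multiple / high volume metastasis is: >3 metastatic lesions", and section 4.2 (Inclusion criteria) has "Stage M1, with multiple / high volume metastasis:More than three (>3) metastatic lesions". Both count extrapelvic nodes, bone and viscera. The Summary has "prostate cancer with >3 skeletal or visceral metastatic lesions on the PSMA-PET/CT", which leaves out nodes.
- **Subgroups.** Section 2 plans "Analysis of response in different subgroups of patients: high versus low tumour load" and gives no cut-off.

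**The concern.** The split is coarse. A man with 4 iliac lesions and a man with 30 vertebral lesions, neither with visceral disease, are both low. A man with 6 bone lesions, one of them in a rib, and a man with 100 are both high. Differences in extent within each level stay outside the base model.

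The primary claim is one of added value, so it is only as good as the base model. Suppose that lesion count predicts CRPC and is also related to upfront PSMA response after allowing for PSA and ADT response. The response term can then carry the part of extent that the split misses. A positive test would be read as showing that response on the third scan is informative, when part of the signal was already on the baseline scan. That matters in practice, because the baseline scan is standard of care and the response scans are the additional ones.

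**Working it through.** **1. The plan's own figure.** Inputs from section 4.2 (Sample size calculation): SD 4 and HR 1.2 (the low end of 1.2–1.3), both per 10 percentage points; R² 0.75; two-sided 5%; power 80%; event probability 0.5.

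Events D = (1.960 + 0.842)² / [SD² × ln(HR)² × (1 − R²)], and N = D / 0.5.

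- R² 0.75: D = 7.849 / (16 × 0.03324 × 0.25) = 59.0, so N = 119.
- R² 0.80: D = 73.8, so N = 148.

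The stated 150 is therefore reached at R² 0.80, the upper end of the Fig. 2 caption, and not at the 0.75 given in the text. With N = 150 the expected events are 150 × 0.5 = 75.

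**2. What a two-level split keeps.** If log load is normal and cut so that a share p is high, the split keeps φ(z)² / [p(1 − p)] of its variance. This is 0.64 at p = 0.5, 0.49 at 0.8 and 0.34 at 0.9. The planned split also depends on site and visceral disease, so it follows the count less closely. Under two assumed lesion-count distributions truncated at more than 3, with 64% and about 80% of men high, it kept about 34% and 28% of the variance of log count.

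**3. Does the lost part reach the primary test?** Trials of 150 men with about 75 events were simulated. PET response had no effect of its own, so the likelihood ratio test should reject in 5%. The documents give neither the load hazard ratio nor the correlations, so these are assumptions.

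| Base model and assumed link | Load HR per SD | High/low split | Continuous load |
|---|---|---|---|
| Load only; correlation with response 0.3–0.5; 60% / 80% / 90% high | 1.5 | 4–11% / 9–18% / 11–24% | 4–6% |
| PSA and ADT response added; load acts only through ADT response | range tried | 4–7% | 4–7% |
| PSA and ADT response added; upfront response carries load directly | 1.3–1.5 | 5–12% | 4–7% |
| Same | 2.0 | up to 27% | 4–7% |

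The first row is not the planned model, which has five further factors. The other rows are closer to it. A separate set, with PSA correlated 0.5 with load and an ADT response that itself carries load, agrees: 5–7.5% at HR 1.5 and 6–13% at HR 2.0 with the split.

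**4. Limiting cases.** A further set let ADT response explain 75% of the variance of upfront response. It imposed a residual load–response correlation of 0.3–0.5, with no allowance for PSA taking up part of load.

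- With the split, rejection was 8–17%, 16–32% and 25–60% at load HR 1.3, 1.6 and 2.0. With log count it was 4–6%.
- The spurious PET hazard ratio was about 1.03–1.15 per 10 points, against the planned 1.2.
- With load unrelated to CRPC, or unrelated to upfront response, rejection was 5–7% with the split and 5–8% with log count. The Monte Carlo error is about 1 point, so there is no excess.

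**5. Cost in power.** Power = Φ(√[75 × 16 × 0.03324 × (1 − R²)] − 1.96), where 75 × 16 × 0.03324 = 39.9.

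| R² with finer load | Square root | Power at N = 150 | N for 80% |
|---|---|---|---|
| 0.75 | 3.158 | 88% | 119 |
| 0.80 | 2.825 | 81% | 148 |
| 0.82 | 2.680 | 76% | 164 |
| 0.85 | 2.446 | 69% | 197 |

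**The case against.** The plan asks a prediction question: what response adds to factors already in use. The volume split is an established clinical classifier, taken from a cited trial. If PET response improves on the usual factors, rejection is the right answer to that question, whatever the source of the information. The base model also contains PSA terms and ADT response as a continuous percentage, which can absorb load. PERCIST response is a percentage change in SUV, and nothing in the documents says that it follows lesion count. Baseline PET has its own secondary analysis. A raw count has problems too: section 5.2.1 gives no counting rule for confluent disease and allows different tracers between centres.

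Much of this stands. The split is a defensible known predictor and should stay, and the excess is small or absent in several plausible settings. But section 7.1 would attribute any gain to response. With extent held only at two levels, a reader cannot tell response from baseline extent, and a separate secondary analysis of the baseline scan does not settle it.

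A reader might infer that the entry rule of more than three lesions causes the under-adjustment or empties the low group. It does neither. Men with 4 or 5 bone lesions, bone disease confined to pelvis and vertebrae, or extrapelvic nodes only still fall in the low level, and two-level coding would lose information under any entry rule.

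**Conclusion.** The point holds as a cheap improvement to the primary models, not as a demonstrated error in the test. The documents establish three things: extent enters at two levels only, finer data are recorded, and the claim is one of added value. They do not establish the size of any bias. With PSA and ADT response in the model it ranges from none to modest at a load HR of 1.3–1.5 per SD (rejection 4–12%). It is larger, up to 27%, only if load is strongly prognostic and acts directly on upfront response. It vanishes if either link is absent. The simulations made the hazard log-linear in load, so the good result with continuous load assumes that form.

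Two stronger readings are not supported. The false-positive rates of up to 24% come from a model adjusting for load alone, which the trial will not fit. And no passage draws conclusions about men with three or fewer lesions, so the two uses of high volume, the subgroup label and the missing nodes in the Summary are matters of wording.

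**What to change.** **Primary models (sections 4.2 and 7.1).** Keep the clinical volume split as the known predictor. Add log(number of metastatic lesions on the baseline PSMA-PET/CT) to both Cox models, specified before analysis and with a stated counting rule for confluent disease. The likelihood ratio test and c-statistic then measure what response adds beyond baseline PET extent, and the test of response keeps its degrees of freedom. The simulations used continuous load in place of the split. Keeping both leaves the count in the model and retains comparability with earlier studies.

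**Cost.** No new data are needed. One degree of freedom is added to both models: if every factor takes one, the larger model goes from 7 to 8 terms on about 75 events, or from 75/7 = 10.7 to 75/8 = 9.4 events per term. R² may rise, so recheck it with the count included and restate N or power from the table above.

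**Editorial.** Give the two definitions of high volume different names. Describe the load subgroups as within men with more than three lesions, and state their cut-off. Reconcile the Summary's eligibility wording with section 4.2 (Inclusion criteria).

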5.2.1.2 Timing second PSMA-PET/CT – hormonal therapy response

Second PSMA-PET/CT needs to performed 2 months after start of hormonal therapy (+/- 1 week). As per guidelines recommendations, upfront therapy needs to be started <3 months after start of hormonal therapy.

5.2.1.3 Timing third PSMA-PET/CT – upfront therapy response Third PSMA-PET/CT needs to be performed 2 months after start of upfront therapy (+/- 1 week).

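### The base-model factor for early PSA response is defined only as a nadir with no time window, which permits PSA values from after the third scan

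*Combined protocol and SAP*

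**What the plan says.** Section 7.1 sets up the primary analysis as two nested Cox models for time to CRPC. The base model holds six factors, the last three being "PSA early response, type of upfront therapy, PSMA response to hormonal therapy only". The second model adds PERCIST PSMA response after the start of upfront therapy. The models are compared by a likelihood ratio test, and "the c-statistic will be calculated to estimate the added benefit of PERCIST PSMA response above the known predictors of CRPC".

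For the factors, section 7.1 points back to a section 4.4. The list it means is printed under 4.2, Sample size calculation. The PSA entry there is "PSA response (defined as PSA nadir", with no start, end or landmark date.

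Section 2 also names the factor without a date: "PET findings, PSA at diagnosis, pathological Gleason score, tumour load, and PSA early response". For PET, the same section does give a period: "PSMA-PET/CT early response assessment (between start of upfront therapy and after 2 months of upfront therapy".

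Section 3 provides for PSA at monthly outpatient checks. In section 5.1.1 the biochemical arm of the CRPC definition is measured against the nadir, again without a window. The radiological arm does not use it.

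**The concern.** The primary analysis asks what the third scan adds to what is already known about a patient. That requires every base-model factor to be known by the date of that scan. A nadir over all follow-up is not: even a low value seen before the scan can be called the nadir only once later values are in.

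There is a second difficulty. A minimum can only stay the same or fall as values are added. Patients who remain CRPC-free for longer have more values, so part of any link between a low nadir and a long time to CRPC could arise by construction. The nadir is also the reference level for biochemical CRPC.

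If the base model carries such information, the likelihood ratio test and the change in c-statistic answer a different question from the stated one. A real contribution of PET could be hidden, or an apparent one created.

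**Working it through.** The plan gives no figure for this point. The check covers what the text defines and whether a literal nadir can reach past the scan.

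**1. The definition, section by section.**
- Section 2: named as early PSA response; no time point.
- Section 4.2 (Sample size calculation): defined as PSA nadir; the word early is absent and there is no time point.
- Section 7.1: named as early PSA response; definition deferred to the list in 4.2.

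An analyst coding from the plan would find one operational definition, and it has no cut-off.

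**2. When the third scan falls, in months from the start of ADT.** Section 5.2.1.2 puts the second scan at 2 months ± 1 week and says "upfront therapy needs to be started <3 months after start of hormonal therapy". Section 5.2.1.3 says "Third PSMA-PET/CT needs to be performed 2 months after start of upfront therapy (+/- 1 week"). Assume that upfront therapy starts no earlier than the second scan, and take 1 week as 0.23 months.
- Earliest: (2 − 0.23) + (2 − 0.23) = 3.54
- Latest: 3 + 2 + 0.23 = 5.23

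At one PSA per month, 3 to 5 values exist by the third scan.

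**3. How many values a literal nadir can draw on.** For biochemical CRPC at month m, the last three values are the required rises and cannot be the nadir. At most m − 3 candidates remain, and fewer if the rise lasts longer than three visits. A patient still CRPC-free at study end has 48 − 18 = 30 to 48 months of follow-up (section 3 duration; section 4.2 accrual of about 18 months).

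| Patient | Candidate values | Of these, after the third scan |
|---|---|---|
| Biochemical CRPC at month 12 | at most 9 | 9 − 5 = 4 to 9 − 3 = 6 |
| Biochemical CRPC at month 18 (median in section 1) | at most 15 | 15 − 5 = 10 to 15 − 3 = 12 |
| Biochemical CRPC at month 24 (median in section 4.2) | at most 21 | 21 − 5 = 16 to 21 − 3 = 18 |
| CRPC-free at study end | 30 to 48 | 30 − 5 = 25 to 48 − 3 = 45 |

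The literal definition can therefore use post-scan values, and the number available depends on the outcome. The table counts opportunities. It does not show where nadirs fall.

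**4. What a change of PSA measure could do to power.** Section 4.2 plans with an R² between PET response and the other factors. With N = (1.96 + 0.8416)² / [SD² × (ln HR)² × (1 − R²)] / 0.5, HR 1.2 and SD 4, the result is 119 at R² 0.75 and 148 at R² 0.80. The second is close to the planned 150 and lies at the upper end of the Figure 2 caption. With 150 × 0.5 = 75 events, power = Φ(√(75 × 16 × (1 − R²)) × ln 1.2 − 1.96), which gives 0.885 at R² 0.75, 0.806 at 0.80 and 0.687 at 0.85. The R² of 0.85 is an illustrative value beyond the documents' range. They do not say how R² would change with the PSA measure.

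**The case against.** The strongest reply is that the word early already sets a limit. Sections 2 and 7.1 both use it, and section 2 gives early PET response an end point 2 months into upfront therapy. On that reading the authors meant PSA over a similar period, and the entry in section 4.2 is loose wording. This stands in part: no section says that post-scan PSA will be used. It does not close the gap, because the limit is written for PET and not for PSA. The second scan, the start of upfront therapy and the third scan would all fit the word, and the choice could be made after outcomes are known.

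A second reply is that the lowest PSA may often precede the third scan, in which case a windowed and an unwindowed nadir coincide. The documents give no PSA course, so this can be neither confirmed nor excluded.

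A reader might infer that the primary comparison, as planned, does test PET against later PSA, or that most nadirs fall after the scan because most candidate values do. The documents support neither. The first turns a missing window into an instruction, and the second treats every monthly value as equally likely to be the lowest. A simulated size of bias would reflect whatever PSA course was assumed.

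**Conclusion.** The point holds as a defect of definition in the primary analysis. A base-model factor has one operational definition, without a window and at odds with its own name. Followed literally, it lets information from the outcome period into the model against which PET is judged. That goes beyond missing detail, because it affects what the likelihood ratio test and c-statistic estimate.

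Confidence is high that the window is missing and that post-scan values are permitted. The consequence is only a possibility: neither its direction nor its size can be derived from the documents. The timing and counts assume PSA at monthly checks only, upfront therapy starting no earlier than the second scan, and accrual of up to 18 months within the 48. It should be fixed before any outcome data are analysed.

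**What to change.** In the factor list of section 4.2 (Sample size calculation), replace the PSA entry by a definition with a cut-off no later than the third scan, for example: *PSA early response: lowest PSA from start of ADT up to and including the date of the third PSMA-PET/CT.* Percent change from the PSA at diagnosis up to the same date would also serve; the cut-off is the necessary part. Use the same definition in sections 2 and 7.1, correct the cross-reference to section 4.4, and state that the whole-follow-up nadir is descriptive only.

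No new data or visits are needed. PSA is already taken monthly, and the cut-off date exists for everyone analysed, since the analysis set is "all subjects who actually receive baseline and two follow-up PSMA PET/CT scans". The time origin and analysis set are unaffected.

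There are two costs. Some PSA information is lost from the base model. The R² between PET response and the base factors may also differ from the planning value in either direction, so power at N = 150 should be rechecked with the windowed measure.

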5.4 Replacement of individual subjects after withdrawal

. Patients who drop out before acquisition of baseline and two response PSMA-PET/CT scans will be replaced. If the endpoint CRPC is not reached due to lost-to-follow-up, patients will be censored at the time of last follow-up.

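### Section 4.2 pairs SD 4, R² 0.75 and HR 1.2-1.3 with 150 patients, but those inputs need 119 at HR 1.2 and 58 at HR 1.3; 150 fits R² 0.80, and the Fig. 2 caption's lower end of 130 fits neither stated R²

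*Combined protocol and SAP*

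**What the plan says.** Section 4.2 (Sample size calculation) names its method: "Sample size estimation was performed in SAS (version 9.4) PROC POWER, using a score test for a Cox proportional hazards model". Its list of considerations gives 80% power, a two-sided 5% type I error, R² 0.75 and a hazard ratio of 1.2 to 1.3 per 10 percentage points of PERCIST PSMA response. It also gives "Probability of event within 24 months: 0.5" and, for the spread of the covariate, "Standard deviation PERCIST PSMA response: 3.5 4 (per 10 percentage points".

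The conclusion drawn from these is: "Assuming a standard deviation of 4, an R² of 0.75, and a hazard ratio of 1.2-1.3, the number needed to include is 150".

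The Fig. 2 caption in the same section uses a wider range of R² and reports a range of sample sizes: "Considering small effect HR 1.2 - 1.3, SD 4, R-square 0.75 - 0.80 leads to sample size 130 - 150".

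The section states no allowance for dropout.

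**The concern.** For a continuous covariate in a Cox model, the required number falls as the hazard ratio moves away from 1 and rises as R² rises. A single N attached to a range of hazard ratios should therefore be the N at the weakest effect, HR 1.2. If the sentence's inputs give a different number there, the text does not record the scenario on which the study was sized.

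What is at stake is the margin. If R² 0.75 is the true basis, 150 leaves 31 patients beyond the requirement. If R² 0.80 is, it leaves 2. An ethics committee or a later analyst judging a recruitment shortfall would need to know which applies, and the printed sentence points to the more comfortable case.

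**Working it through.** **Inputs, all from section 4.2.** Two-sided alpha 0.05 (z = 1.960), power 0.80 (z = 0.842), event probability p = 0.5, SD 4 or 3.5 in units of 10 percentage points, R² 0.75 or 0.80, HR 1.2 or 1.3 per unit.

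**Formula** (Cox score test, continuous covariate):

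events = (1.960 + 0.842)² / [SD² × (ln HR)² × (1 − R²)], and N = events / p.

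The numerator is 7.849, (ln 1.2)² = 0.03324 and (ln 1.3)² = 0.06884.

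**The sentence (SD 4, R² 0.75).**

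- HR 1.2: 7.849 / (16 × 0.03324 × 0.25) = 59.03 events; N = 118.06, so 119.
- HR 1.3: 7.849 / (16 × 0.06884 × 0.25) = 28.51 events; N = 57.01, so 58.

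The largest N over the stated HR range is 119. Reaching 150 with the other inputs fixed would take HR 1.176, which is outside the range. Other conventions do not recover 150 at HR 1.2 either: one-sided alpha gives 93, 85% power gives 136 and 90% power gives 159.

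**The caption (SD 4, R² 0.75 to 0.80).**

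| R² | HR 1.2 | HR 1.3 |
|---|---|---|
| 0.75 | 118.06 → 119 | 57.01 → 58 |
| 0.80 | 147.57 → 148 | 71.27 → 72 |

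The upper end of 150 is reproduced, to rounding, at R² 0.80 and HR 1.2. The lower end of 130 appears in no cell. At HR 1.2 it needs R² of about 0.773, which lies between the two stated values but is neither of them. Neither HR 1.3 value comes near the printed range.

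**Power at 150 patients.** Events = 150 × 0.5 = 75, and power = Φ[ln HR × SD × √(events × (1 − R²)) − 1.960]. At HR 1.2 and SD 4:

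- R² 0.75: 0.1823 × 4 × √18.75 − 1.960 = 1.198, so 88.5%.
- R² 0.80: 0.1823 × 4 × √15 − 1.960 = 0.865, so 80.6%.

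**The other listed SD (3.5, with R² 0.75 and HR 1.2).** 7.849 / (12.25 × 0.03324 × 0.25) = 77.10 events; N = 154.20, so 155. Power at 150: 0.1823 × 3.5 × √18.75 − 1.960 = 0.803, so 78.9%.

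**The case against.** The best defence is that 150 is traceable within the section. The considerations are tied to Fig. 2, the caption carries R² up to 0.80, and the conservative corner of its inputs gives 148, which anyone would round to 150. On that view the sentence merely prints the lower R² where the upper one was used. This largely stands, and it limits the point: a reader might infer that the caption fails altogether or that 150 has no documented source, and neither is supported. What it does not rescue is the sentence as printed, the 130, or the inclusion of HR 1.3 in the caption.

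A second defence is an unstated allowance for loss: inflating 119 for 20% dropout gives 149. The documents give no such rate. Section 5.4 replaces patients lost before all three scans, and for later losses says "If the endpoint CRPC is not reached due to lost-to-follow-up, patients will be censored at the time of last follow-up", which is a censoring rule and not an inflation factor. An allowance cannot be excluded, but it is obtained only by solving backwards from 150, whereas R² 0.80 is printed.

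A third caution is that the Fig. 2 graphic is not available here. The 130 may have been read from a plotted curve at an intermediate R². The caption therefore has to be checked against the figure before it is changed.

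**Conclusion.** The point holds for the sentence and for the lower end of the caption. The sentence's inputs need 119 patients at HR 1.2, so the printed 150 is 26% higher (150/119 = 1.26). The likeliest explanation is that 150 belongs to R² 0.80 and HR 1.2; only the software output can confirm it.

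A reader might infer that the study is underpowered. The mismatch does not show that. At SD 4 and HR 1.2, 150 patients reach 80% power at either R², and the error runs in the conservative direction. The 78.9% at SD 3.5 is a sensitivity result for a value that the sentence and caption do not use. It shows why the SD bullet should be settled, and is not a consequence of the arithmetic slip. That bullet may simply have lost a dash between its two values in the PDF text.

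These figures rest on the standard Cox score-test formula and on the plan's own event probability of 0.5 at 24 months (75 events). Follow-up beyond 24 months would add events and raise power.

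**What to change.** Keep 150. Look up the existing PROC POWER output and Fig. 2, then make three corrections in section 4.2.

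1. State the single HR, SD, R² and event probability behind 150. If R² 0.80 was the basis: *At SD 4, R² 0.80, HR 1.2 per 10 percentage points and event probability 0.5, 148 patients give 80% power; 150 are planned.* If R² 0.75 stands: *At SD 4, R² 0.75, HR 1.2 per 10 percentage points and event probability 0.5, 119 patients give 80% power; the planned 150 give 88.5%.* If the output shows some other input, print that one and recompute on it.
2. Correct the caption to 119-148 at HR 1.2 (58-72 at HR 1.3), once checked against the figure, and make the R² in the list of considerations agree with the sentence.
3. Say in the SD bullet which value was used. If 3.5 is kept as an alternative, add that at R² 0.75 and HR 1.2 it needs 155 patients and that 150 give 78.9% power.

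The cost is a look at existing output and edits to one sentence, the list and one caption. No patients are added and the analysis is unchanged.
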